6.2.1 Primary Efficacy Analysis

The primary efficacy endpoint, symptomatic skeletal event-free survival (SSE-FS), will be defined separately for each of the two efficacy evaluations described above, as follows:

For Comparison 1, SSE-FS following randomization is defined in ITT subjects as the time from randomization to an SSE or death, whichever occurs first. Refer to Appendix 9.1.1 for censoring rules.

For Comparison 2, SSE-FS from 6th dose is defined in W24 subjects as the time from Week 24 baseline (the 6th dose date) to an SSE or death, whichever occurs first. Refer to Appendix 9.1.1 for censoring rules.

For both evaluations, a symptomatic skeletal event (SSE) is defined as follows:

- The use of external beam radiotherapy (EBRT) to relieve skeletal symptoms
- The occurrence of new symptomatic pathological bone fractures (vertebral or non-vertebral)
- The occurrence of spinal cord compression
- A tumor related orthopedic surgical intervention.

The censoring rules for SSE-FS for each comparison are summarized in [Table 9–1](#) and [Table 9–2](#) of [Appendix 9.1.1](#). Stratified statistical tests described in this section refers to two of the three randomization strata as determined by the IXRS: use of prior chemotherapy (≤ 1 regimen versus > 1 regimen), and total ALP (< 220 U/L versus ≥ 220 U/L). Note that Average worst pain score (WPS) was included as one of stratification factor for randomization in order to balance the baseline pain across three arms. However, WPS will not be included in the analysis to avoid sparse cells due to relatively small sample size within each arm.

Each analysis will use a stratified log-rank test. A one-sided significance level of 0.10 will be used for interpretation of the results. Additionally, the hazard ratio (respectively high dose/standard dose and extended dose/standard dose) will be computed together with the two sided -80% and -95% CIs using a stratified Cox regression model. There will be no adjustment for multiple comparisons.

SSE-FS will also be summarized using Kaplan-Meier [5] estimates. Kaplan-Meier [5] curves will be generated, and median survival time together with the 25th and 75th percentiles and associated Brookmeyer-Crowley [6] 80% and 95% CIs will be presented separately for the two comparisons. Kaplan-Meier plots will be presented for the time from randomization for both Comparison 1 and 2. Additionally, similar descriptive summaries will be created for Week 24 population using the randomization baseline.

For each comparison, the contribution of each component of the SSE will be evaluated. Descriptive statistics will be presented.

A Kaplan-Meier [5] curves will be generated for each BMI category (< 18.5 , $\geq 18.5 - < 30$), and ≥ 30) by treatment group within the 2 comparisons. The effect of low baseline BMI status on efficacy will be addressed by including baseline BMI category as a binary covariate (low versus normal/high) in a stratified Cox proportional hazards model.

A 2-compartment Cox model will be fitted as a sensitivity analysis to explore differences between arms A and C for the two time periods before and after the 6th dose, with period as a time-varying covariate. Hazard ratio (and CIs) will be reported for each time period and treatment arm.

Supportive analysis for SSE-FS will be performed for each comparison using a non-stratified log-rank test. The treatment effect (hazard ratio) will be estimated using an unstratified Cox model.

The comparison 2 for SSE-FS will be also performed using randomization baseline as supportive analysis.

As an exploratory analysis, stratified Cox proportional hazards regression models may be fitted for each comparison including other applicable baseline covariates considered to be of prognostic importance. Time-dependent covariates that may be investigated individually in the model include: non-study systemic anti-cancer therapy, increase in analgesics use, radiological progression, pain progression, and pain improvement.

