- To evaluate time to radiological progression
- To evaluate radiological progression-free survival (rPFS)

Exploratory objectives:

- To evaluate quantitated whole body technetium-99 bone scan tumor burden area and index, and determine bone tumor response
- To explore the impact of patient body size on the efficacy and safety of radium-223 dichloride
- Time to increase in physical symptoms of disease based on the NCCN FACT-P Symptom Index-17 (NCCN-FACT FPSI-17) physical disease related symptoms (FPSI-DRS-P) subscale score measured up to Week 48 after the start of treatment
- To evaluate laboratory indicators of efficacy, including:
 - PSA response
 - Time to PSA progression
 - ALP response
 - Time to ALP progression

- Percentage change in ALP from baseline
- To evaluate change in analgesic use.

[figure not shown]
3. Study Design

This is a three arm, randomized, open-label Phase II study of radium-223 dichloride 50 kBq/kg (55 kBq/kg after implementation of NIST update) versus 80 kBq/kg (88 kBq/kg after implementation of NIST update) , and versus 50 kBq/kg (55 kBq/kg after implementation of NIST update) in an extended dose schedule in subjects with castration-resistant prostate cancer metastatic to the bone. Approximately 360 subjects will be randomized in this study.

The randomization will be stratified by use of prior chemotherapy (≤ 1 regimen versus > 1 regimen), by total ALP (< 220 U/L versus ≥ 220 U/L), and by average worst pain score (WPS) of the Brief Pain Inventory – Short Form (BPI-SF) (WPS ≤ 4 versus WPS > 4).

A schematic of the study design is presented in [Figure 3–1](#).

Figure 3–1: Study Design Schematic

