The following body descriptors will be summarized as described in Green and Duffull (2004) [3]:

- Total body weight(TBW), defined as the weight (kg) used for calculating the first dose
- Total body weight (W24), defined as the Week 24 baseline weight (kg)
- Body Mass Index, and Body Mass Index (W24), calculated as:

$$BMI = \frac{Weight (kg)}{[Height (m)]^2}$$

- Ideal Body Weight(IBW) will be calculated as:
 $IBW = 50.0 + [0.89 \times (HT(cm)-152.4)]$ for male

Subjects will be classified by BMI as low weight ($BMI < 18.5$), normal weight ($18.5 \leq BMI < 30$), or high weight ($BMI \geq 30$) at each baseline [4]. Baseline BMI will also be categorized as low versus normal/high.

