6.6 Examination of Subgroups

Subgroup analyses will be conducted for the primary efficacy endpoint SSE-FS following randomization based on the ITT population, and SSE-FS following Week 24 baseline on the W24 population, and for secondary endpoint OS. Subgroup analyses will be provided by subgroup within each respective pooled treatment grouping, as described for the primary analysis for each comparison. Descriptive statistics and hazard ratio estimates with 80% and 95% CIs will be provided at least for the subgroups listed below, provided there is a sufficient number of events (at least 10 events) in total within the subgroup across the applicable pooled treatment groups. Hazard ratios by subgroup with 80% and 95% CIs will be plotted using forest plots.

- ECOG performance status at baseline (0 vs 1)
- Extent of Disease (number of bone lesions: <6, 6-20, >20 or superscan at baseline)
- Race (White, Asian and Other)
- Age group (<65, 65-74, 75-84, >=85 years)
- Baseline Total Body Weight and Ideal Body Weight normalized dose quartiles
- Randomization stratification factors:

- use of prior chemotherapy (≤ 1 regimen versus > 1 regimen)
- total ALP (< 220 U/L versus ≥ 220 U/L)
- average worst pain score (WPS) of the BPI-SF at screening assessment (WPS ≤ 4 versus WPS > 4).
- BMI
 - Low, non-low (< 18.5 and ≥ 18.5)
 - Non-high, high (< 30 and ≥ 30)
- Gleason Score at the time of diagnosis (< 8 , ≥ 8 , Missing)
- Baseline PSA values by median ($< \text{median}$, $\geq \text{median}$)
- Received prior anti-androgens at baseline: abiraterone or enzalutamide (Yes vs. No)

For time-to-event endpoints, Kaplan-Meier [5] estimates will be presented with median, 25th, and 75th percentile survival time and associated 80% and 95% Brookmeyer-Crowley [6] confidence intervals (CI), and number and percentage of censored observations.

Corresponding Kaplan-Meier curves will also be plotted. A Cox proportional hazards model will be fitted for each time-to-event secondary efficacy endpoint, with baseline BMI category coded as a binary covariate (low versus non-low).

Safety analysis (i.e. AE) will be conducted based on age subgroup, and ideal body weight normalized dose quartiles.

7. Document history and changes in the planned statistical analysis

- SAP 21 February 2016 version 1.0
- SAP 17 May 2017 version 2.0

Table 7–1 The Changes Between SAP V1.0 and SAP V2.0

Endpoints/Definitions	SAP V1.0	SAP V2.0

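### The Cox models in SAP 6.2.1 and 6.6 enter body size only as a main effect of BMI below 18.5, so they give a prognostic contrast and no estimate of whether body size changes the treatment effect (minor)

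*SAP*

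**What the plan says.** The objective in SAP Section 2 is: "To explore the impact of patient body size on the efficacy and safety of radium-223 dichloride".

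The SAP approaches it in these places:

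- **6.1.2** defines three BMI classes ("Subjects will be classified by BMI as low weight" below 18.5, normal from 18.5 to below 30, high from 30) and a two-way split, low versus normal/high.
- **6.2.1**, for SSE-FS, plans Kaplan-Meier curves for the three classes "by treatment group within the 2 comparisons". It then names a stratified Cox model: "The effect of low baseline BMI status on efficacy will be addressed by including baseline BMI category as a binary covariate (low versus normal/high").
- **6.6** names a Cox model for each secondary time-to-event endpoint, "with baseline BMI category coded as a binary covariate (low versus non-low").
- **6.6** also plans hazard ratios with 80% and 95% CIs for SSE-FS and OS within subgroups. These include "Low, non-low (< 18.5 and ≥ 18.5"), "Non-high, high (< 30 and ≥ 30") and "Baseline Total Body Weight and Ideal Body Weight normalized dose quartiles". They are required only where a subgroup has at least 10 events in total. Adverse events are tabulated by quartile of ideal-body-weight normalized dose.

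No treatment-by-BMI term, no continuous BMI or weight term, and no interaction estimate for the subgroups is stated anywhere.

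**The concern.** The impact of body size on efficacy is a question about effect modification: does the treatment hazard ratio differ between small and large men? A model with treatment and a BMI indicator, but no product term, forces one treatment hazard ratio on everyone. Its BMI coefficient answers a different question, namely whether low-BMI men do better or worse than others whatever their arm. Section 6.2.1 nevertheless presents this model as the one that addresses efficacy.

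The study report could therefore present a prognostic hazard ratio for being underweight as a finding about efficacy. It could also take a coefficient near 1 as evidence that size does not matter. Because normal and high weight are merged, these two models also say nothing about heavy men.

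**Working it through.** **Inputs.** From SAP 3.4: 360 men randomized 1:1:1; 186.61 expected events and hazard ratio 0.667 (Comparison 1, Arm B against pooled A and C); 74.91 expected events and hazard ratio 0.606 (Comparison 2); one-sided 0.10. From SAP 3.3: a minimum of 135 events for Comparison 1. From SAP 6.6: the 10-event rule. The share of men with BMI below 18.5 is not given and is varied below.

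**1. The plan's own figures.** The SAP has no figure for the BMI analysis, so the check is on power. With the Schoenfeld formula, power = Φ(√(D·a(1−a))·|ln HR| − 1.2816), where D is the number of events and a the allocation share:

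- Comparison 1, a = 1/3: √(186.61 × 2/9) = 6.44; 6.44 × 0.405 − 1.28 = 1.33; power 90.8% (SAP: 90.5%).
- Comparison 2, a = 1/2: √(74.91/4) = 4.33; 4.33 × 0.501 − 1.28 = 0.89; power 81.2% (SAP: 80.6%).

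The event counts are a sound basis for what follows.

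**2. What the main-effect coefficient measures.** Suppose low BMI has no prognostic effect, but the treatment hazard ratio is 1.5 times higher in low-BMI men. In Comparison 1 only the high-dose third carries that difference, so the coefficient averages to about exp(ln 1.5 / 3) = 1.14. A simulation (200 trials per scenario, n = 360, allocation 1:2, unstratified Cox, assumed low-BMI share 25%, median estimates) gave:

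| Truth | BMI HR, main-effect model | Treatment HR, main-effect model | Ratio of HRs, interaction model |
|---|---|---|---|
| Prognostic 1.5, no modification | 1.49 | 0.68 | 1.07 |
| Prognostic 1.5, modification 1.5 | 1.70 | 0.75 | 1.49 |
| No prognostic effect, modification 1.5 | 1.15 | 0.75 | 1.54 |

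The main-effect BMI hazard ratio follows prognosis. It cannot tell a modification of 1.5 from a mild prognostic effect of 1.15. The interaction model separates the two. The 25% share and the simplified censoring make this an illustration of direction only.

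**3. When the low-BMI subgroup hazard ratio must be shown.** If events occur in proportion to numbers, the share needed for 10 SSE-FS events is:

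- Comparison 1: 10/186.61 = 5.4%, or 10/135 = 7.4% at the minimum count.
- Comparison 2: 10/74.91 = 13.3%.

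The SAP gives no OS event count, so the same step cannot be done for OS.

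**4. An interaction at the 18.5 cut alone.** SE = √(1/(d₁·a(1−a)) + 1/(d₂·a(1−a))), with d₁ and d₂ the events below and above the cut. The ratio of hazard ratios detectable with 80% power is exp((1.2816 + 0.8416)·SE).

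| Assumed share below 18.5 | Comparison 1 | Comparison 2 |
|---|---|---|
| 3% | 5.6 events, SE 0.91, ratio 6.9 | 2.2 events, SE 1.35, ratio 17.7 |
| 5% | 9.3 events, SE 0.71, ratio 4.5 | 3.7 events, SE 1.06, ratio 9.5 |
| 10% | 18.7 events, SE 0.52, ratio 3.0 | 7.5 events, SE 0.77, ratio 5.1 |

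Multiplying the existing indicator by treatment would therefore add little unless the low-BMI share is large.

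**5. An interaction with continuous BMI.** Per SD, SE = 1/√(D·a(1−a)): 1/6.44 = 0.155 and 1/4.33 = 0.231. For a normal distribution the 10th and 90th percentiles lie 2.56 SD apart. The 80% CI factor for the ratio of treatment hazard ratios between them is exp(1.2816 × 0.155 × 2.56) = 1.66 in Comparison 1 and exp(1.2816 × 0.231 × 2.56) = 2.13 in Comparison 2.

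**The case against.** The strongest reply is that the SAP does look at the treatment effect by body size. Section 6.6 plans treatment hazard ratios with CIs for SSE-FS and OS on both sides of BMI 30 and by normalized-dose quartile, and 6.2.1 plans Kaplan-Meier curves by BMI class and arm. A quarter of the events is about 47 in Comparison 1 (186.61/4) and 19 in Comparison 2 (74.91/4), so quartile subgroups of about that size would clear the 10-event rule. Safety is covered by quartile as well. The objective is exploratory, in a phase II trial.

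Most of this stands. A reader might infer that the two Cox models are the only model-based body-size analysis and that the objective goes largely unanswered. The subgroup hazard ratios show otherwise. They leave no estimate, with an interval, of how much the treatment effect differs by size. The quartiles also have limits. Section 6.1.4 defines total-body-weight normalized dose as activity divided by weight, which for a drug dosed per kg reflects the assigned dose more than size. Section 6.6 does not say whether quartiles are cut within arm. In Comparison 2, where both arms receive the same activity per kg, the ideal-body-weight quartiles are informative.

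Two further inferences should be resisted:

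- That the low-BMI group is only a handful of men. The SAP gives no BMI distribution; this follows only from an assumed small share.
- That a continuous interaction is far more precise because its per-SD interval is narrow. Comparing one SD with a whole-group contrast is not like for like; step 5 gives the fairer figure.

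Nor is there a need to drop the pre-specified low-BMI contrast, which uses cut-offs the SAP cites.

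**Conclusion.** The point holds as a minor one. The BMI coefficient in both named models is prognostic. It cannot do what 6.2.1 says it does, and the plan contains no interaction estimate for any measure of body size. The other planned analyses address effect modification descriptively, for SSE-FS and OS only. On the SAP's expected event counts, and with events proportional to numbers, the SSE-FS hazard ratio below 18.5 need not appear if the low-BMI share is under about 5.4% (Comparison 1) or 13.3% (Comparison 2).

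No primary or secondary test, event count or decision rule is affected. Since every arm receives radium-223, even a correct interaction would show only whether size modifies the high-dose or extended-dose effect relative to standard dose. It would not show how size affects the efficacy of radium-223 as such.

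**What to change.** In SAP 6.2.1 and 6.6:

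- Add, for each comparison, a stratified Cox model with treatment, continuous baseline BMI (or total body weight) and their interaction.
- Report the interaction, and the treatment hazard ratio at chosen percentiles such as the 10th, 50th and 90th, with 80% and 95% CIs.
- Keep the low-BMI covariate model, but describe its coefficient as prognostic.
- State that the interaction concerns modification of the high-dose or extended-dose effect relative to standard dose.

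The Kaplan-Meier curves and subgroup hazard ratios can stay as they are.

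The cost is SAP wording and one further model per endpoint, with no new data, since height and weight are already collected. The model assumes a log-linear size effect, which a quadratic term can check. Precision remains limited (80% CI factors of about 1.7 and 2.1, as in step 5), so the result should be read as exploratory.

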- Symptomatic skeletal event free survival from the 6th dose (SSE-FS2) for the "standard dose" vs. "extended dose" comparison (Comparison 2)

Two analyses of efficacy and safety are planned in this study:

- A final analysis to occur after the latest of the following maturation criteria are met:
 - 135 SSE-FS (SSE-FS1) events in subjects included in Comparison 1
 - 75 SSE-FS (SSE-FS2) events following the 6th dose in subjects included in Comparison 2
 - The last subject has been followed for 30 days from last treatment.
- An updated analysis to occur after the last subject has completed the active follow-up period in this study for two years following last dose of Ra-223 dichloride (if after primary endpoint cut-off).

Additional details on the timing of the analyses are described in Section 3.3 below.

This Statistical Analysis Plan (SAP) specifies the analyses and data presentations planned for both the final and the updated analysis.

This SAP was written based on the following documentation:

Document	Date	Version
Protocol	9 August 2013	1.0
Protocol Amendment no. 1	20 November 2013	2.0
Protocol Amendment no. 2	16 August 2015	3.0
Protocol Amendment no. 3	16 May 2017	4.0

2. Study Objectives

Co-primary objectives:

- To evaluate efficacy as measured by SSE-FS of radium-223 dichloride 50 kBq/kg (55 kBq/kg after implementation of NIST update) every 28 days for up to 6 doses

compared to radium-223 dichloride 80 kBq/kg (88 kBq/kg after implementation of NIST update); and

- To evaluate efficacy as measured by SSE-FS of radium-223 dichloride 50 kBq/kg (55 kBq/kg after implementation of NIST update) every 28 days for up to 6 additional doses compared to no further radium-223 dichloride treatment in subjects with CRPC metastatic to the bone who previously received radium-223 dichloride 50 kBq/kg (55 kBq/kg after implementation of NIST update) every 28 days for up to 6 doses, and survived SSE free and are eligible for further radium-223 dichloride treatment.

Symptomatic skeletal events (SSEs) are defined as:

- The use of external beam radiotherapy (EBRT) to relieve skeletal symptoms
- New symptomatic pathological bone fractures (vertebral and non-vertebral)
- Tumor-related orthopedic surgical intervention
- Spinal cord compression

Secondary objectives:

- To evaluate safety and tolerability
- To evaluate overall survival (OS)
- To evaluate pain improvement rate
- To evaluate time to pain progression
- To evaluate time to first SSE

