4.5 Data Rules

4.5.1 Determining Baseline Values

This study has two distinct baselines for efficacy analyses, the randomization baseline and the Week 24 baseline.

Randomization baseline value for efficacy parameters: is defined as the last non-missing value on or before the date of randomization.

Week 24 baseline: Unless otherwise specified, the ‘Week 24 baseline’ is defined as the date of the 6th injection. This baseline is defined only for those subjects who are eligible for Comparison 2 analyses. That is, subjects who had received at least 6 injections.

Week 24 baseline value for efficacy parameters: Unless otherwise specified, the ‘Week 24 baseline value’ is defined as the last non-missing value on or before the date of the 6th injection.

Ideally, this visit would be the date of the 7th injection for Arm C subjects and expected 7th injection date for Arm A subjects. However, the end of treatment visit (30±7 days from last dose) for Arm A subjects could be missing due to consent withdrawal or happen out of visit window. Hence, there is no comparable visit for Arm A subjects that could be used as the expected 7th injection date.

To account for this and achieve comparability between the two arms, the 6th injection date is used as the reference date for Comparison 2 subjects. It should be noted that this could lead to a somewhat dilution of the treatment effect in Arm C due to an early reference date.

Baseline value for safety parameters: is defined as the last non-missing value on or before the date of first dose.

4.5.2 Pooling cut-off date for Arm C subjects in Comparison 1

For Comparison 1, Arm C subjects are planned to be pooled with Arm A subjects. This pooling will be done such a way that only comparable data from Arm C subject pooled. The following algorithm will be used to identify the cut-off date for pooling:

Arm C: Pooling cut-off date = $7*28 + \text{randomization date}$; for subjects that were randomized but not treated,
= $(7-x)*28 + \text{last dose date}$; for $1 \leq x \leq 6$,
= 7th dose date; for $x \geq 7$,
where x be the number of injections received.

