4.7 Additional Statistical Considerations

4.7.1 Delayed Effect Efficacy Assumptions

Since the comparison between the “standard” and “extended” regimens involves identical treatment for the first 6 doses, the following assumptions were made:

- Both regimens have identical efficacy for the first 6 doses, and
- The efficacy would diverge at the time that extended-dosing subjects received their 7th dose.

This feature is consistent with a delayed effect as described in Fine (2007) [1] and Zhang and Quan (2009) [2]. To account for this delayed-effect feature, hazards were modeled using a 2-compartment approach:

- With the standard (Arm A) and high-dose (Arm B) regimens having constant hazards throughout the study, and
- The extended regimen (Arm C) initially having the same hazards as the standard regimen (Arm A) but having a fixed change point at Week 24, approximately the point at which the 7th dose would begin, with constant, reduced hazards thereafter.

A sensitivity analysis using two-compartment Cox model will be performed by taking into account of this delayed-effect feature for Comparison 2. The details are specified in Section 6.2.1.

5. Analysis Sets

- **Intent-to-treat (ITT):** All randomized subjects. The ITT population will be used in the analysis of efficacy endpoints for Comparison 1. Subjects will be included in ITT analyses according to the treatment to which they were randomized as based on IXRS. The randomization baseline will be used in the ITT analyses.
- **Week 24(W24):** All ITT subjects in Arm A (standard dose) and Arm C (extended dosing) treated with radium-223 dichloride and eligible for further treatment at W24 (i.e., 7th injection). Week 24 applies to subjects who received the 6th injection without any dose delays. As dose delays are allowed per protocol, 6th injection can occur after Week 24 for subjects who had dose delays. Hence, this population is defined based on the number of injections not based on the timing. The W24 dataset

will be used for the analysis of efficacy endpoints related to Comparison 2 and associated evaluations. Subjects will be included in W24 analyses according to the treatment to which they were randomized.

- **Safety (SAF):** All subjects who have received at least one study drug administration. This safety population will be used in the analyses of all safety endpoints. Subjects will be included in the analyses according to the treatment they received.

6. Statistical Methodology

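### The delayed-effect Cox sensitivity model for Comparison 2 splits time at the 6th dose, not at the 7th where the SAP assumes the arms diverge, so its later-period hazard ratio is modestly diluted

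*SAP*

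**What the plan says.** Section 4.7.1 assumes that the two regimens are equally effective over the first six doses. It then states: "The efficacy would diverge at the time that extended-dosing subjects received their 7th dose". Its hazard model describes Arm C as "having a fixed change point at Week 24, approximately the point at which the 7th dose would begin". The same section closes with a commitment, "A sensitivity analysis using two-compartment Cox model will be performed by taking into account of this delayed-effect feature for Comparison 2", and refers to Section 6.2.1 for the specification.

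Section 6.2.1 specifies the model as comparing Arms A and C "for the two time periods before and after the 6th dose, with period as a time-varying covariate", with a hazard ratio for each period. It does not name the analysis set.

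Section 4.5.1 explains why the Week 24 baseline is the 6th-injection date. The end-of-treatment visit in Arm A may be missing or out of window: "Hence, there is no comparable visit for Arm A subjects that could be used as the expected 7th injection date". It accepts the price: "this could lead to a somewhat dilution of the treatment effect in Arm C due to an early reference date".

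Section 4.5.2, written for pooling Arm C into Comparison 1, projects a 7th-dose date without needing a visit. The date is last dose + (7−x)×28 days for 1 to 6 injections, and randomization + 7×28 days for untreated subjects.

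**The concern.** The model is meant to represent a change point at the 7th dose, but it is specified with a change point one dosing interval earlier. No section reconciles the two. By the SAP's own assumption the arms have equal hazards between the 6th and 7th doses, so events in that interval pull the later-period hazard ratio toward 1.

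The primary Comparison 2 analysis also starts at the 6th dose. A sensitivity model with the same split inherits the same dilution, when it could have given an estimate closer to the effect of doses 7 to 12. If the co-primary result is weak, readers will look to this model for that estimate.

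**Working it through.** **Inputs.** From Section 3.4: control median 9 months; hazard ratio 9/14.85 = 0.606 after Week 24; 3% loss per month; 74.91 events; one-sided alpha 0.10; power 80.6%; accrual about 16 months; cut-off at 39.1 months. From Section 2: further doses "every 28 days for up to 6 additional doses". Assumptions made here: exponential hazards, a month of 30.4375 days, and no dose delays unless stated.

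**1. Reproduce the SAP's power.** Schoenfeld: Φ(√74.91/2 × |ln 0.606| − 1.2816) = Φ(4.328 × 0.501 − 1.2816) = Φ(0.886) = 81.2%, against 80.6% stated. A 4,000-replicate simulation of the design, with divergence at Week 24 and an assumed linear 7-month ramp-up, gave 132.7 subjects, 74.9 events, 79.0% power and cut-off at 39.7 months. The SAP gives 132.8, 74.91, 80.6% and 39.1. The assumptions are therefore read correctly.

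**2. Locate the split.** The 6th dose falls 5×28 = 140 days (Week 20) after the first, and the 7th falls at 6×28 = 168 days (Week 24). The gap is L = 28/30.4375 = 0.920 months.

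**3. Choose the follow-up range.** The last subject has about 39.1 − 16 = 23.1 months from randomization. Less 140/30.4375 = 4.6 months, that leaves about 18.5 months after the 6th dose. Earlier subjects have longer. Values of 18 to 30 months are used.

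**4. Share of events in the identical-treatment interval.** Let λ = ln2/9 = 0.0770, λ_E = 0.606λ = 0.0467 and c = −ln 0.97 = 0.0305. Write P(h, t) = h/(h+c) × [1 − exp(−(h+c)t)].

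- Events in the gap, both arms: 2P(λ, L)
- Events afterwards: exp(−(λ+c)L) × [P(λ, F−L) + P(λ_E, F−L)]

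At F = 24 months the gap gives 0.135, and the remainder gives 0.906 × (0.657 + 0.503) = 1.051. The share is 0.135/1.186 = 11.4%. The event-weighted hazard ratio is exp[(1 − 0.114) × ln 0.606] = 0.642.

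| Follow-up after 6th dose (months) | Share of events in first 28 days | Expected later-period HR | Power at 75 events |
|---|---|---|---|
| 18 | 12.5% | 0.645 | 73.1% |
| 24 | 11.4% | 0.642 | 73.9% |
| 30 | 10.8% | 0.640 | 74.3% |

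**5. Check by simulation.** In the same replicates, a Cox fit from Week 24 gave a geometric mean hazard ratio of 0.608. A fit from the 6th dose (Week 20) gave 0.644, with 84.7 events and 75.2% log-rank power.

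**6. Compare with precision.** With 75 events, SE(ln HR) ≈ 2/√75 = 0.23. The shift is ln(0.642/0.606) = 0.058, about a quarter of one SE. The 95% interval around 0.606 runs from roughly 0.39 to 0.95.

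**7. Allow for delay.** Section 5 says that dose delays are allowed but gives no figure. If the 7th dose came 42 to 56 days after the 6th (assumed range), the hazard ratio from a 6th-dose split would be 0.656 to 0.682 over 18 to 30 months.

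**The case against.** The 6th-dose reference is deliberate and disclosed. Section 4.5.1 adopts it for Comparison 2, gives the reason and admits the dilution, so Section 6.2.1 can be read as following that convention. The model still places about 20 of the 24 weeks of identical dosing in the earlier period. It is exploratory, with no decision rule attached.

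The points about size and status stand. The point about rationale does not fully carry over: the lack of a comparable Arm A visit matters for a baseline value, whereas a Cox split needs only a date.

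Four stronger readings are tempting but not supported:

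- *That no other analysis bears on the question, or that this model cannot tell an early reference date from a lack of effect.* Section 6.2.1 also plans Kaplan-Meier plots from randomization, which show descriptively where the arms separate. A shift of a quarter of an SE would seldom change the reading.
- *That period membership depends on treatment received, because subjects who stop early have no 6th-dose date.* This holds only if all Arm A and C subjects are fitted. Section 4.7.1 ties the model to Comparison 2, whose subjects have at least six injections. The documents leave the set unstated.
- *That Section 4.5.2 already supplies the date.* That rule covers Arm C only, for Comparison 1 pooling, and uses the actual date once a 7th dose is given. It has to be adapted.
- *That dilution reaches 15% of events (hazard ratio 0.653).* This needs 12 months of follow-up, which is shorter than the planned timeline implies.

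**Conclusion.** Sections 4.7.1 and 6.2.1 disagree on the change point, and the version in 6.2.1 gives an estimate biased toward no effect. On the SAP's assumptions the expected later-period hazard ratio is about 0.64 instead of 0.606, a loss of about 11% to 12.5% of the log hazard ratio. Delay of the 7th dose would increase the loss. The figures rest on exponential hazards, an effect that starts exactly at the 7th dose, and 18 to 30 months of follow-up.

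A reader might infer that the co-primary test of Comparison 2 is affected. It is not: this is a sensitivity model, and the early start of the primary analysis is a separate choice that Section 4.5.1 discloses. The inconsistency should be corrected because doing so is cheap, but its consequence is modest.

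**What to change.** In Section 6.2.1, replace the 6th-dose split with a projected 7th-dose date, computed identically in Arms A and C, and report the arm hazard ratio before and after it. For subjects in the W24 set this is the 6th-dose date + 28 days, whether or not a 7th dose was given.

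State the analysis set. If all randomized Arm A and C subjects are to be included, use last dose + (7−x)×28 days for those with 1 to 5 doses and randomization + 7×28 days for untreated subjects, in line with Section 4.5.2. Keep 6th dose + 28 days for everyone with six or more.

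The cost is one sentence and one derived variable. The later period will hold slightly fewer events (in the simulation, about 75 instead of about 85 at the same cut-off). Some dilution remains where the actual 7th dose comes later than projected.
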